Heading out of the contradictory results, no publication has reported the in vivo comparison between Papacarie duo and the newly developed CMCR agent Brix 3000 gel in terms of their clinical and radiographic success and their antimicrobial effect compared to the Art approach for caries removal in young immature permanent teeth. The null hypothesis of this study is that no statistically significant difference will be detected between both materials and ART approach regarding to their clinical performance, and their antimicrobial effect in young permanent molars during the follow up period.

AIM OF THE STUDY

Primary aim

- To assess and compare the effectiveness of two chemo-mechanical agents Brix 3000 and Papacarie duo in terms of their clinical and radiographic success in young permanent molars, in comparison with ART approach.

Secondary aims

- Determine the required time for complete caries removal for each method.
- Evaluation of patients' subjective pain reactions following each method.
- Evaluation of antimicrobial effect of two chemo-mechanical caries removal agents by comparing the colony forming units (CFU) at the treatment visit before and after the application of each agent compared to hand excavation method.

MATERIALS AND METHODS

Study design

This will be a randomized, parallel, three-arms controlled clinical trial, with a 1:1:1 allocation ratio. It will be set up and reported according to the CONSORT guidelines.⁽³⁰⁾

The PICOT question is:

Will children (8-10 years old) with class I carious lesion in the first permanent first molar (with ICDAS score 5 or 6) (population; P) using Brix 3000 or Papacarie duo gel (intervention; I) for Chemo-mechanical caries removal in comparison with ART approach (Hand excavation) (Control; C) show a greater success (outcome; O) at different time intervals over twelve months period (time; T)?

Study setting and location

The study will take place in the Department of Pediatric Dentistry and Dental Public Health at the Faculty of Dentistry and the Department of Microbiology and Immunology at the Faculty of Pharmacy, Alexandria University, Alexandria, Egypt.

Sample

Sample size estimation

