- No local anesthesia will be administered as it would alter the pain perception of the patient unless necessary.

Evaluations

1. Clinical evaluation

- The clinical assessment will be at 3-, 6- and 12-month intervals to evaluate
 - a) Postoperative pain
 - b) Any signs or symptoms of pulpitis
 - c) Vertical and horizontal percussion tests
 - d) Tooth-color alterations and fistulas presence.
 - e) Restoration success will be evaluated according to the criteria of atraumatic restorative treatment by Phantumvanit et al. (1996) (45). It is based on the retention of the material in the cavity and the presence of secondary caries.
 - f) Restorations which will receive a score of 0, 1 or 7 will be considered successful while those having a score of 2, 3, 4 or 8 will be considered failures. Those which will receive a score of 5, 6 will be excluded from the analysis (Appendix IV).

2. Radiographic evaluation

- Periapical radiograph will be taken immediately after clinical procedure and at 6- and 12-months intervals during follow up period to confirm the clinical evaluation.⁽⁴⁶⁾
- It will be obtained by the long cone paralleling technique to minimize the distortion using the film holders.⁽⁴⁷⁾
- The radiographic evaluation will be performed using the radiographic subtraction method and the assessment of the density of the remaining dentin by gray-scale analysis using the Image j 1.37 V program⁽³¹⁾.
- Therefore, a greater degree of density on the image will indicate a greater success.

- Any case that will exhibit pulp involvement associated with a radiolucent image or any signs for periapical lesions will be considered unsuccessful treatments.

3. Evaluation of time required to perform procedure

- The time needed for complete caries removal will be recorded for each caries removal method.
- The timing of each procedure will set immediately upon the first application by using a stopwatch and turned off when there is no carious dentin left in the cavity.
- After complete removal of decay, the teeth will be restored with glass ionomer filling as a temporary restoration to be replaced after the follow up period using Composite filling sandwich technique.

4. The participants' pain assessment:

- Subjective pain will be assessed after caries removal by means of Wong-Baker faces scale⁽⁴⁸⁾. It consists of faces with different facial expression for happiness and pain and is scored from 0-5 as 0 is very happy and feels no pain and 5 is very painful (APPENDIX III).

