- Each child will be trained to use the scale by first modeling and then asking each participant to think of the last time she/he felt something painful' and to select the facial expression that best represented his/her experience of discomfort.

5. Microbiological evaluation Procedure

- Samples from the carious lesion will be collected prior to and following complete caries removal for detection of the change in bacterial count (Streptococci and Lactobacilli counts).

a. Sample dilution

All samples will be dispersed by vortexing for 30 seconds then 10-fold serially diluted using sterile saline. A measure of the dilution will then be used for traditional plate culturing methods. ⁽⁴⁹⁾

b. Culture

Aliquots of 10 ml of each dilution will be inoculated into freshly prepared Rogosa agar media using a micropipette.

- Mitis Salivarius agar plates will be incubated anaerobically in an atmosphere containing 10% CO₂ at 37°C for 72 hours to detect Streptococcus mutans count
- Rogosa agar plates will be incubated aerobically at 37° C for 48 hours to detect Lactobacilli count.

c. Isolation and Enumeration

Following the predetermined incubation period, colonies grown on the specified media will be counted and represented as (CFU/ml). Streptococcus mutans will be identified based on their characteristic morphology on Mitis Salivarius agar plates. Similarly, Lactobacilli will be identified biochemically and microscopically on the basis of their morphology.

Colony count

The number of colonies will be determined and expressed as colony forming units using the following equation. ⁽⁵⁰⁾

$$\text{CFU/ml} = \frac{\text{n}^\circ \text{ of colonies} \times \text{dilution factor}}{\text{Volume taken in ml}^{(51)}}$$

6. Oral Health quality of life questionnaire

- Oral health quality of life will be assessed at one week recall appointment by using the Arabic validated version of the child perceptions questionnaire. ⁽⁵²⁾
- It consists of 25 items distributed among 4 domains: oral symptoms, functional limitations, emotional well-being, and social well-being. It is self-reported by children using a 5-point Likert scale (APPENDIX V), and responses range from 0–4 for each item. Hence, total scores range from 0 to 100, and higher scores indicate poorer OHRQoL. (APPENDIX VI)

STUDY OUTCOME

Treatment effect will be evaluated after the follow up period by comparing:

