- 1- Clinical effectiveness of each material during the follow up period at 3-, 6- and 12-months intervals confirmed with radiographic findings at 6- and 12-month intervals.
- 2- Timing required for complete caries removal following each caries removal method
- 3- Participants' subjective pain reaction following each caries removal method.
- 4- Antimicrobial effect of both CMCR agents by comparing the colony forming units (CFU) at the treatment visit before and after application of each agent compared to conventional caries removal method.

Follow up

All patients will be recalled after 3-, 6- and 12-month intervals. On the day of the recall appointment, patient preparation will be done as mentioned before.

Outcome assessment

- 1- Restorations which will receive a score of 0, 1 or 7 will be considered successful while those having a score of 2, 3, 4 or 8 will be considered failures.
- 2- Any clinical sign and symptoms teeth with pain, intraoral or extra oral abscess formation and fistula formation will be recorded as unsuccessful treatments
- 3- Any periapical lesions on radiography during follow-up will be recorded as unsuccessful treatments.

Study Plan

[figure not shown]

Figure 1: Flow chart of the study plan

STATISTICAL ANALYSIS

The statistical Package for Social Sciences (SPSS)* version 27.0 for Windows will be used for data analysis.

All data will be collected; The Chi square test will be used to compare the difference between the three groups regarding the clinical success, the T-test or the Mann-Whitney U test will be used to analyze the differences between the microbiological samples. The data will be graphically presented with suitable graphs. The level of statistical significance will be set at 5%.

* SPSS Inc., Chicago, IL, USA

ETHICAL CONSIDERATIONS

1. The research protocol will be approved by the Research Ethics Committee of Alexandria University Faculty of Dentistry (IRB No. 001056 –IORG 0008839) prior to any research-related activities.
2. All research activities involving human subjects will abide by the Declaration of Helsinki⁽⁵³⁾ and other ethical guidelines adopted by the Research Ethics Committee of Alexandria University Faculty of Dentistry.
3. Benefits:
 - It will provide caries treatment for young permanent molars in children using minimally invasive atraumatic procedures.
 - It will allow overcoming the disadvantages of conventional treatment with local anesthesia

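### The one study null hypothesis joins the primary outcome with the secondary antimicrobial outcome at an unadjusted 5%, so its false-rejection rate is about 19% to 24%

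*Combined protocol and SAP*

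**What the plan says.** The Aim of the Study ranks the outcomes. The primary aim compares the gels "in terms of their clinical and radiographic success in young permanent molars, in comparison with ART approach". The secondary aims are time to caries removal, subjective pain, and "Evaluation of antimicrobial effect of two chemo-mechanical caries removal agents by comparing the colony forming units (CFU) at the treatment visit", before and after removal and relative to hand excavation.

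The null hypothesis that closes the Introduction does not follow this ranking. It says that "no statistically significant difference will be detected between both materials and ART approach regarding to their clinical performance, and their antimicrobial effect", and it refers to the follow-up period, although CFU is measured only at the treatment visit.

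Statistical Analysis says "The Chi square test will be used to compare the difference between the three groups regarding the clinical success" and names no visit. For the bacterial counts, "the T-test or the Mann-Whitney U test will be used to analyze the differences between the microbiological samples". It adds "The level of statistical significance will be set at 5" per cent. It gives no order of testing, no division of the 5%, no adjustment and no rule for which result decides the study null. Evaluations, item 5, shows that two counts are analysed: samples are taken for "detection of the change in bacterial count (Streptococci and Lactobacilli counts".

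**The concern.** A null that denies a difference on two outcomes is contradicted by a significant result on either one. Each bacterial count is tested at the full 5%, by two-group tests in a three-arm trial, so the chance of at least one false positive under that null is well above 5%. Most of the excess comes from the secondary outcome.

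At stake is what a rejected null would mean. The sample size rests on one-year success alone. As worded, one same-day CFU comparison could lead to a report that the gels differ from ART when the outcome the trial was sized for shows nothing. This is separate from testing success at several visits: it remains if success is tested once, at 12 months, at exactly 5%.

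**Working it through.** **The plan's own figure.** Sample size estimation gives 30 per group for 95% versus 67% success, 5% alpha and 80% power. With a pooled variance and a two-sided test, the mean proportion is 0.81 and

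n = [1.96·√(2·0.81·0.19) + 0.8416·√(0.95·0.05 + 0.67·0.33)]² / 0.28² = (1.087 + 0.436)² / 0.0784 = 29.6, so 30.

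The figure reproduces. It uses the whole 5% for success and leaves nothing for CFU.

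**Inputs from the documents**
- Level: 5% per test (Statistical Analysis). Sidedness is not stated, so two-sided is assumed.
- Success: one three-group chi-square, 2 degrees of freedom, taken as done once.
- CFU: two-group tests on two counts. Each gel against ART gives 2 × 2 = 4 tests. All arm pairs give 2 × 3 = 6.
- Three equal arms (Study design, 1:1:1).

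**Assumptions the documents do not settle.** No true differences; CFU tests between arms; one sample pair per child; each test valid on its own; correlation of 0 to 0.8 between any two outcomes in the same child.

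**Upper bound, all tests independent**
- Success plus four CFU tests: 1 − 0.95⁵ = 22.6%.
- Success plus six CFU tests: 1 − 0.95⁷ = 30.2%.

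The real rates are lower, because pairwise tests share arms and outcomes in a child are correlated.

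**Simulation allowing for both** (400,000 runs per setting). In each run, three arm means are drawn for success and for each count, with the given correlation between outcomes. Success is rejected when the sum of squared deviations of the three standardised means exceeds 5.99. A CFU pair is rejected when the standardised difference exceeds 1.96 in absolute value. The success test alone rejects 5.0% of the time, so rejection on CFU alone is the total minus 5.0.

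| Correlation | Four tests: null rejected | Of which CFU alone | Six tests: null rejected | Of which CFU alone |
|---|---|---|---|---|
| 0 | 21.5% | 16.5% | 26.8% | 21.8% |
| 0.5 | 19.1% | 14.1% | 23.8% | 18.8% |
| 0.8 | 15.6% | 10.6% | 19.3% | 14.3% |

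**If the sentence is read as two nulls.** The chance of at least one false CFU result is 17.3% down to 13.9% for four tests, and 22.7% down to 18.4% for six, over the same correlations.

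**The case against.** The strongest reply is that the ranking is clear elsewhere. The aims carry primary and secondary headings, the PICOT question asks only about success, the trial is sized on success, and CFU is fourth in the outcome list. No sentence says that one significant test rejects the whole null or decides the trial, so the null can be read as two statements judged separately. This stands in part: a CFU result would not overturn the clinical part, and the documents do not show that the ranking has been abandoned. But the antimicrobial part would still be tested four or six times at 5%, and nothing in the plan says which reading applies.

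A second reply is that the microbiological tests might be before-and-after comparisons within each arm, since samples are taken at both points. The calculation above would then not apply. The secondary aim and the outcome list, however, compare the gels with the control method, which needs between-arm tests.

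Two stronger readings are tempting and should not be drawn:
- A reader might infer that the null would be rejected on CFU about five times in six. That is not a rejection rate. It approximates the share of false rejections due to CFU alone, and only with six independent tests: 0.95 × 26.5% = 25.2%, and 25.2/30.2 = 83%. With shared arms the share is 68% (10.6/15.6) to 77% (16.5/21.5) for four tests and 74% (14.3/19.3) to 81% (21.8/26.8) for six.
- A reader might add time and pain to the count. Both are already labelled as secondary aims, neither is named in the null, and Statistical Analysis specifies no test for them.

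**Conclusion.** The point holds. The stated null covers a primary and a secondary outcome, and no rule controls its error rate at the 5% the plan sets. Under the assumptions listed, it is falsely rejected about 19% of the time (15.6% to 21.5%) with four gel-versus-ART CFU tests, or 24% (19.3% to 26.8%) with six. That is roughly three to five times the stated level. In about 11% to 22% of such trials the rejection would rest on CFU with no difference in success. If the two parts are judged separately, the success part keeps its 5% and the antimicrobial part has an error rate of 14% to 17% (four tests) or 18% to 23% (six tests).

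The figures depend on the between-arm reading, on a single success test and on the assumed correlations. They do not show that the trial would usually reject its null by chance, or that the primary aim has been displaced. They show that the hypothesis, as worded, does not match the aims and is not held at 5%.

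**What to change.** - **Introduction, null hypothesis:** limit the study null to the primary outcome, and state the antimicrobial effect as a separate secondary hypothesis tied to the treatment visit, where it is measured.
- **Statistical Analysis, primary outcome:** state that only this outcome decides the trial, tested once at 12 months by the three-group chi-square at 5%. If each gel is instead tested against ART, adjust the two contrasts by Holm, because two unadjusted contrasts sharing one control have an error rate of about 9%.
- **Statistical Analysis, CFU:** say that the comparisons are between arms and adjust them together by Holm at 5% as secondary claims. There are four gel-versus-ART tests, or six if Brix 3000 is also compared with Papacarie duo.
- **Time and pain:** leave them as the secondary aims they already are.

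The study null then has a 5% false-rejection rate, and the CFU family is held at 5% separately. The change is wording only, with no extra children, samples or visits. The price is that the smallest CFU p-value must be below 0.05/4 = 0.0125, or 0.05/6 = 0.0083 with six tests, so a borderline CFU result could no longer be called significant.

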The sample size was estimated assuming a 5% alpha error and 80% study power. The overall success rate after 1 year was 95% for chemo-mechanical caries removal,⁽³¹⁾ whereas it was 67% for traditional caries removal.⁽³²⁾ Based on the difference between independent proportions, the sample size was calculated to be 30 patients per group, increasing to 36 patients to make up for lost follow-up cases. Total sample = number per group x number of groups = 36 x 3 = 108 patients.

Software

The sample size was based on Rosner's method⁽³³⁾ calculated by G*Power 3.1.9.7. ⁽³⁴⁾

Eligibility criteria

The participants enrolled in this study will be selected after fulfilling the following criteria:

Inclusion Criteria

- Healthy children aged 8-10 years old.
- The presence of at least one deep carious class 1 lesion in the first permanent molar with a score of 5 or 6 according to the International Detection and Assessment System (ICDAS), detected by visual-tactile inspection to assess lesion severity. ⁽³⁵⁾ (APPENDIX I, Tables 1)

Exclusion criteria

- Children reporting spontaneous or elicited pain from caries or showing any signs of pulpal infection, swelling or abscess.
- Pulpal exposure or bleeding during the excavation procedure
- Children presenting with special health care needs or undergoing medical treatment for chronic or acute diseases affecting salivary flow.
- Allergy or sensitivity to any of the materials included in the study.

Randomization technique and allocation⁽³⁶⁾

- Subjects complying with the inclusion criteria will be randomly assigned to one of the treatment groups, using a computer-generated list of random numbers to either the Brix 3000, Papacarie duo gel group (www.random.org) or ART approach (Hand excavation).
- Allocation will be performed by a trial independent individual and the allocation ratio is intended to be equal (1:1:1).

Allocation concealment⁽³⁷⁾

An assistant will be responsible for giving each participant a serial number that will be used for his/her allocation. A duplicate of this number will be kept in an opaque envelope indicating to which group the patient belongs. This envelope will be kept by a trial independent individual who will be assigned the role of opening it only at the time of intervention; so that the group to which the child is allocated is concealed from the investigator. Grouping Participants will be randomly and equally allocated to one of the three treatment groups:

Grouping

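### The stated 80% power covers each gel against ART, not the Brix 3000 versus Papacarie duo comparison that is also part of the primary aim

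*Combined protocol and SAP*

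**What the plan says.** All references are to the combined protocol and SAP.

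- **Primary aim (Aim of the study).** The aim is "To assess and compare the effectiveness of two chemo-mechanical agents Brix 3000 and Papacarie duo" on clinical and radiographic success, and the sentence ends "in young permanent molars, in comparison with ART approach". It therefore covers gel against gel and gel against ART.
- **Rationale (last paragraph of the Introduction).** It states that "no publication has reported the in vivo comparison between Papacarie duo and the newly developed CMCR agent Brix 3000 gel", with ART named as the further comparator.
- **Null hypothesis (same paragraph).** It is that "no statistically significant difference will be detected between both materials and ART approach".
- **PICOT question (Study design).** It is framed against ART only: will either gel, "in comparison with ART approach (Hand excavation) (Control; C) show a greater success (outcome; O")?
- **Sample size estimation.** The calculation was made "assuming a 5% alpha error and 80% study power". The inputs are one class-level rate, "The overall success rate after 1 year was 95% for chemo-mechanical caries removal", and 67% for traditional removal. The result is 30 per group, raised to 36 for losses. The source cited for the 95% is, by its title in the reference list, a Papacarie trial. No separate Brix rate, gel-to-gel difference or margin is given.
- **Statistical analysis.** Clinical success is compared across the three groups by one chi-square test at 5%. No pairwise comparison, confidence interval or equivalence procedure is described.

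**The concern.** A reader of the rationale and the primary aim will expect an answer on Brix 3000 against Papacarie duo, and will take the unqualified 80% power to cover it. The calculation behind that figure contains no difference between the gels, so it says nothing about the chance of detecting one.

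The gap matters at the interpretation stage. The null hypothesis is phrased as a test result, that no significant difference will be detected, so a non-significant p-value satisfies it literally. With low power and no planned interval, nothing in the plan would show the reader how large a difference between the gels remains compatible with the data. The comparison presented as new is then the one on which the trial is least informative.

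**Working it through.** **Inputs.** Success 95% and 67%, alpha 5%, power 80%, 30 per group raised to 36 (Sample size estimation); allocation 1:1:1 (Study design). Sidedness is not stated; two-sided is assumed. The loss rate is not stated; 36 × (1 − 1/6) = 30, so 30 and 36 per arm bracket the planned loss and no loss.

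**Step 1: reproduce the plan's figure.** Two proportions, pooled variance, no continuity correction, with p̄ = (0.95 + 0.67)/2 = 0.81:

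n = [1.96·√(2·0.81·0.19) + 0.8416·√(0.95·0.05 + 0.67·0.33)]² / 0.28² = (1.0874 + 0.4362)² / 0.0784 = 29.6, so 30 per group.

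Power at 30 per group is 80.5%, and at 36 it is 87.4%. (A one-sided calculation with continuity correction also gives 30; the two-sided corrected version gives 37.) The stated size is therefore right for 95% against 67%, that is, for each gel against ART.

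**Step 2: power for gel against gel.** The plan names no gel-to-gel difference, so the lower rates below are assumptions, with 95% kept for the other gel. The exact columns sum binomial probabilities over all outcomes for which the uncorrected two-arm chi-square gives p ≤ 0.05. The last column uses the formula in step 1.

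| Success rates | Exact power, 30 per arm | Exact power, 36 per arm | n per arm for 80% power |
|---|---|---|---|
| 95% vs 90% | 11% | 13% | 435 |
| 95% vs 85% | 26% | 32% | 141 |
| 95% vs 80% | 45% | 53% | 76 |
| 95% vs 75% | 63% | 72% | 49 |
| 95% vs 70% | 78% | 85% | 36 |

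Fisher's exact test would be weaker: 2%, 9% and 24% at 30 per arm for the first three rows.

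**Step 3: smallest gap with 80% power.** By the plan's formula, the second gel would have to succeed in only 67.2% at 30 per arm (a gap of 27.8 points) or 70.4% at 36 per arm (24.6 points).

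**Step 4: precision if both gels succeed in about 95%.**

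- Wald half-width, 1.96·√(2·0.95·0.05/n): 0.110 at n = 30 and 0.101 at n = 36.
- Wald is too narrow here, with about 0.05 × 30 = 1.5 expected failures per arm. With equal observed counts, the Newcombe half-width is √[(p − l)² + (u − p)²], where l and u are the Wilson limits of one arm.
- 28/30 in each arm: Wilson limits 0.787 and 0.982, half-width 0.154. 29/30 in each arm: 0.136.
- 34/36 in each arm: 0.132. 35/36 in each arm: 0.116.

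So the interval is about ±10 to 11 points by Wald and ±12 to 15 points by Newcombe.

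**Step 5: what the planned test answers.** Under 95/95/67, p̄ = 2.57/3 = 0.857. The noncentrality at 30 per arm is 30·[2·(0.0933)² + (0.1867)²]/(0.857·0.143) = 12.8 on 2 degrees of freedom, which gives about 90% power. All of that comes from the ART arm. A significant three-group result would not show whether the gels differ, and a non-significant one would not show that they are alike.

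**The case against.** The strongest reply is that the trial is really about gel versus ART. The aim sentence ends with ART, the PICOT question and the null hypothesis are set against ART, and the sample size matches that reading exactly. This stands. A reader might infer that the sample size, or the 80% power as such, is wrong; step 1 shows that it is not. The gap is confined to the Brix versus Papacarie part of the aim.

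Three other inferences also go too far:

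- **That the plan assumes 95% for each gel.** It gives one rate for the class and assigns none to Brix. What can be said is that no gel-to-gel difference is specified.
- **That the head-to-head result will be non-significant whatever the truth.** Step 2 contradicts this: at 30 per arm, power is 45% to 78% for gaps of 15 to 25 points. It is low for gaps of about 10 points or less.
- **That the sponsor intends to report non-significance as equality.** A no-difference null is conventional, and no sentence states such an intention. The wording merely leaves the reading open.

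It is also fair to say that the two-arm test in step 2 is not one the plan names. That adds to the point, since the plan contains no analysis of this contrast at all.

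What the reply does not remove is that the aim says compare, the rationale rests on the missing head-to-head, and no section addresses the precision of that comparison.

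**Conclusion.** The point holds in a limited form. The sample size supports each gel against ART on the plan's own assumptions. It does not support Brix 3000 against Papacarie duo, where power is about 11% to 13% for a 5-point gap, 26% to 32% for 10 points and 45% to 53% for 15 points, and reaches 80% only at a gap of about 25 to 28 points. If both gels succeed in about 95%, a non-significant result could not exclude a difference of 10 points or more in either direction.

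These figures assume a two-sided 5% test, 30 to 36 evaluable children per arm, one outcome per child, and 95% success for the better gel. The documents give no second gel rate, so the gaps are illustrative. The trial remains valid for its powered contrast. The change is worth making because it governs what can be concluded about the comparison presented as new.

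**What to change.** 1. **Sample size estimation:** state that the 80% power applies to each gel against ART (95% against 67%) and not to Brix 3000 against Papacarie duo.
2. **Statistical analysis:** add pairwise risk differences in success with 95% confidence intervals, by Newcombe's or another score method. Report Brix against Papacarie as an estimate.
3. **Same section:** state that a non-significant difference between the gels will not be read as equal effectiveness.

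Moving the head-to-head to a secondary aim would also be consistent with the PICOT question, but it is optional.

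The cost is a few sentences in two sections, with no extra patients, visits or procedures. The downside is a more modest claim for the head-to-head comparison.
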